Studies have shown that social unrest and exposure to community violence have a strong detrimental impact on adolescent mental health (Vorhies, Guterman, & Haj-Yahia, 2011). A supportive family environment is the most consistent mediator of this impact (Cummings et al., 2009). Studies in Northern Ireland, where a significant proportion of adolescents were exposed to community conflict, emotional insecurity and family cohesion predicted subsequent adolescent delinquency and aggression (Cummings et al., 2016; Taylor et al., 2016). Mental health issues, particularly post-traumatic stress (PTS), are common in social unrest, but they are moderated by positive parental mental health and positive parenting (Dubow et al., 2012).

Post-traumatic stress is caused by actual or threatened death or serious injury, direct exposure to violence, witnessing a significant person's exposure to violence or an accident, or indirect exposure through hearing aversive details of the event (American Psychiatric Association, 2013). Core symptoms of PTS include re-experiencing the trauma, avoidance, and a persistent sense of threat. Prolonged PTS may lead to issues with affective dysregulation, negative self-concept, and relationship disturbances (Cloitre et al., 2018). Studies indicate that 6–20% of individuals develop post-traumatic stress disorder after a potentially traumatic event (Kahana et al., 2006). Other mental health issues including depression, anxiety, paranoid ideation, and aggression have been found in adolescents with extensive exposure to community violence (Al-Krenawi & Graham, 2012). Adolescents living with parents who have different life values and exert high psychological control may lack a buffer against the threat of mental health problems during social unrest. Thus, this age group is at the highest risk of developing chronic mental health issues after exposure to traumatic life experiences (de Jong et al., 2015).

Two core mechanisms – security and connection, and emotion regulation – are crucial to adolescent mental health in a context of social unrest. This project aims to support parents so that they can provide a safe and trustful environment to meet adolescents' needs after experiencing traumatic events (Gewirtz, Forgatch, & Wieling, 2008). Given the current social unrest, parents and adolescents need emotion regulation strategies that can promote positive affective change and facilitate empathy and reconciliation in families and communities (Cehajic-Clancy et al., 2016).

The content design of prevention and intervention programmes combines mindfulness skills with psychoeducation as a strategy for promoting security, connection, and emotion regulation (Chambers et al., 2009). Mindfulness training has been widely adopted as a therapeutic approach for reducing emotional distress and promoting psychological well-being, including PTS (Banks et al., 2015; Gu et al., 2015). A study in Israel showed that after being presented with anger-inducing information related to political conflict, participants in a mindfulness workshop were more supportive of conciliatory policies and the effect was mediated by a reduction in perceived threat and improvement in emotion regulation (Alkoby et al., 2017). In emotionally charged situations that may lead to verbal and physical aggression, mindfulness on the soles of the feet is a specific technique that enable individuals to manage their emotional arousal by shifting the focus of attention to a neutral physical body part (Singh et al. 2011). A recent study of Chinese adolescents suggested that teaching parents Mindfulness on the Soles of the feet could reduce the aggressive behaviour of their adolescent children (Ahemaitijiang et al., 2019). A pilot study of Hong Kong secondary school students is in progress.

Hypotheses of the study

The current study will test the following three hypotheses based on the literature:

- (i) Parents participate in a brief mindful parenting program will experience less depressive symptoms, anxiety symptoms, post-traumatic stress symptoms, family conflicts, and higher family functioning and interpersonal mindfulness than parents from wait-list control.
- (ii) Effects of the program will sustain at 3-month follow up.
- (iii) Parents with higher exposure to political unrest will predict the severity of the symptoms at pretest and follow-up.

RESEARCH PLAN AND METHODOLOGY

Study design

This study uses a multi-site, randomized control trial. The effects of this intervention will be tested using a two-arm randomized controlled trial, comparing the mindful parenting program (Arm 1), to waitlist control group (Arm 2). Assessments will be made before (T0), 1-month follow up (T1), and 3-month follow-up (T2). The programme effects will be tested using both between-subject (comparison of the two arms) and within-subject (comparison of measures at T1, T2, and T3).

Sample size estimation. An estimated 340 parents will be recruited and randomised into an intervention group and a waitlist control group. The sample estimation is based on an expected effect size of .33 for family functioning in the PI's pilot study, with an estimated drop-out rate of 15%, a two-tailed α error of 5%, 80% power, and a test of two independent groups.

Recruitment of participants. Inclusion criteria are: (1) parents of an adolescent with the age between 10 to 21; (2) parents with a score of Patient Health Questionnaire (PHQ-9) score of 2 or above. Exclusion criteria are: 1) parents with current self-reported psychiatric diagnoses of psychosis, alcohol or substance abuse, 2) parents experiencing personal or family crisis in last six months; (3) parents cannot speak Chinese.

The research project will be announced and promoted in five non-governmental organizations, and social media. All interested parents will be given an information sheet and a four minute video explaining the nature of the study. After providing consent to participate the study, a research assistant who is blinded to the personal data of the participants, will administer the random assignment using computer generated programming. Participants will be randomly assigned to mindful parenting program (Arm 1), or waitlist control group (Arm 2).

Procedures

Program plan. The themes and content are based on a brief mindful parenting program developed by the same principal investigator (Lo et al., 2016, Lo et al., 2019). Psychoeducation of stress and coping in the context of parenting relationship is infused. Instructors for the program possess a PhD in psychology or social work, a specialist in psychiatry, and foundational professional training in mindfulness-based cognitive therapy.

Implementation and assessment. After the first assessment (T0), caregivers who meet inclusion criteria will be randomized into Arm 1 or Arm 2. After the intervention, two time points will be used to assess the intervention outcome and sustainable effect at one month and three month. Programs are delivered in group format and will be conducted in five sites, including the P-I's university and the service units of NGO collaborators. To ensure intervention fidelity, all program sessions will be audio-recorded and an independent rater will listen to 20% of the selected clips on random basis, and assess whether each element in the intervention protocol has been implemented with consistency. Higher concordance rates will signify greater fidelity to the intervention protocol, which will be carefully monitored throughout the study.

An Ethical approval for this study has been obtained from the Research Office of the Hong Kong Polytechnic University.

Measures

All measures of the variables are summarized in Table 1 below. In line with the study objectives and hypotheses, primary outcome variables include parental depression. Secondary outcome measures include anxiety, post-traumatic stress, perceived family functioning, family conflicts, and interpersonal mindfulness.

Data Analyses

Quantitative data analyses: Intervention effects. All analyses will be carried out according to the intention-to-treat approach. (Moher et al., 2010). MANOVA will be used to evaluate the effects of the mindful

parenting (Arm 1), relative to waitlist control group (Arm 2), and the analyses of the primary and secondary outcome measures. In addition to the immediate programme effects, outcomes measured at T1 and T2 will be compared, to assess whether maintenance effects will be sustained at 3-months.

Table 1. Outcome variables and measures

Study variables and measures
Depression - Measured by the Patient Health Questionnaire (PHQ-9, Kroenke et al., 2001), 9 items
Anxiety - Measured by the Generalized Anxiety Disorder 7-item (GAD-7, Kroenke, et al., 2016), 7 items
Post-traumatic stress - measured by the International Traumatic Questionnaire (ITQ, Cloitre et al., 2009), 6 items
Family functioning - Measured by 5 item, Family APGAR Scale (Smilkstein, Ashworth, & Montano, 1982), with five subscales in adaptation, partnership, growth, affection, and resolve.
Family conflict - measured by Conflict Tactics Scale (CTS-2, Straus & Gelles, 1979), 16 items
Interpersonal mindfulness - measured by the Interpersonal mindfulness in Parenting Scale (Duncan, 2007, Lo et al., 2018).

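### Hypothesis (i) covers six outcomes, but the plan does not say which result decides it, and a significant MANOVA would not show that depression improved

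*Combined protocol and SAP*

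**What the plan says.** Hypotheses of the study, (i), states in one sentence that parents in the programme "will experience less depressive symptoms, anxiety symptoms, post-traumatic stress symptoms, family conflicts, and higher family functioning and interpersonal mindfulness than parents from wait-list control". That is six outcomes.

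Measures separates them, in open wording: "primary outcome variables include parental depression". It continues: "Secondary outcome measures include anxiety, post-traumatic stress, perceived family functioning, family conflicts, and interpersonal mindfulness".

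Implementation and assessment sets the follow-up: "two time points will be used to assess the intervention outcome and sustainable effect at one month and three month".

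Data Analyses gives one method for everything: "MANOVA will be used to evaluate the effects of the mindful" parenting arm against waitlist, and it covers "the analyses of the primary and secondary outcome measures". It adds a comparison of the two follow-up visits to judge maintenance.

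The only error rate is in Sample size estimation: "a two-tailed α error of 5%, 80% power, and a test of two independent groups".

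The document gives no rule for which result settles hypothesis (i), no primary visit, no follow-up step after MANOVA, no testing order or multiplicity adjustment, and no statement that the secondaries are exploratory.

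**The concern.** A MANOVA omnibus test asks whether the arms differ on any combination of the six outcomes. Rejection does not say which outcome moved. The programme trains mindfulness directly, so interpersonal mindfulness could carry the rejection while depression is unchanged. As written, hypothesis (i) could be declared supported on all six outcomes, on depression alone, on the omnibus test, or on a subset that leaves depression out.

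The second issue is the secondary claims. To say anything about anxiety, post-traumatic stress or family conflict, the trial needs a step after MANOVA, and the plan does not describe one. If that step is a separate 5% test on each outcome, the omnibus test limits false claims only while no outcome is truly affected. Once one is, it tends to reject, and the null outcomes are read without adjustment.

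**Working it through.** **Inputs from the document:** six outcomes (one primary, five secondary), two follow-up visits, α = 5% two-sided, 80% power, effect size 0.33 (for family functioning), 15% dropout, 340 parents.

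**Assumed, not in the document:** 1:1 allocation, equal correlation ρ between outcomes, a true effect d on one outcome and none on the other five, and unadjusted two-sided 5% tests on each outcome after a significant MANOVA.

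**Step 1: the plan's own figure.**
- n per arm = 2(1.960 + 0.842)² / 0.33² = 144.2, so 145 per arm and 290 in total.
- 290 / 0.85 = 341.2, so 342, against 340 stated. The figure reproduces.
- Completers: 340 × 0.85 = 289. Noncentrality at d = 0.33 is 0.33 × √(289/4) = 2.805.
- Power at 5%: Φ(2.805 − 1.960) = 80%. Power at 1%: Φ(2.805 − 2.576) = 59%.

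**Step 2: what an omnibus rejection shows.** Six normal test statistics were simulated with 289 completers. The omnibus test rejects when Z′Σ⁻¹Z exceeds the 95th percentile of chi-square on 6 degrees of freedom. With one outcome truly affected, it rejects in this share of trials:

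| d | ρ = 0 | ρ = 0.3 | ρ = 0.5 |
|---|---|---|---|
| 0.33 | 52% | 64% | 80% |
| 0.5 | 91% | 97% | 99% |

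These figures are the same whichever outcome is affected. They therefore apply when depression has no effect at all.

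**Step 3: false secondary claims at one visit.** This is the chance that MANOVA rejects and at least one null secondary has p < 0.05, with the real effect on depression and all five secondaries null:

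| d on depression | ρ = 0 | ρ = 0.3 | ρ = 0.5 | ρ = 0.7 |
|---|---|---|---|---|
| 0 | 4.5% | 4.2% | 3.7% | 3.0% |
| 0.2 | 10.6% | 10.9% | 11.2% | 11.6% |
| 0.33 | 17.8% | 17.9% | 17.1% | 14.7% |
| 0.5 | 22.2% | 20.8% | 18.2% | 14.8% |

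If the real effect is on interpersonal mindfulness instead, only four null secondaries remain. The rate is then 15–18% for d = 0.33–0.5 and ρ = 0–0.5, and about 9% at d = 0.2 and ρ = 0. Over all these settings with one real effect, the range is roughly 9–22%.

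For reference, five independent 5% tests with no MANOVA in front give 1 − 0.95⁵ = 22.6%.

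**Step 4: power if secondaries are tested formally.** Holm's first step over five outcomes uses 0.05/5 = 1%, where power at d = 0.33 is 59% (Step 1). Requiring a significant PHQ-9 result first lowers it further (ρ = 0–0.5):
- PHQ-9 and that one secondary both have d = 0.33: 48–53%.
- All six outcomes have d = 0.33: 57–62%.
- PHQ-9 has d = 0.2 and that one secondary has d = 0.33: 24–31%.

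**The case against.** The strongest reply is that the plan already separates one primary outcome from five secondaries, and that unadjusted secondaries under a single primary are often accepted as supportive. This stands in part. Measures does make the separation, so a reader who infers from hypothesis (i) that all six outcomes have equal standing goes too far. Nor is a single PHQ-9 test at a stated visit inflated by the secondaries. But the plan neither calls the secondaries supportive nor says that PHQ-9 decides hypothesis (i).

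Other replies that limit the point:

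- **A flat error rate.** A reader might infer a false-claim rate of 17–22% per visit. That needs a true effect of 0.33–0.5 on depression, correlation of at most 0.5, and unadjusted 5% follow-up tests. The document gives none of these. If nothing works, a MANOVA gate keeps the rate near 4%.
- **Both visits together.** Five secondaries tested at both visits without MANOVA would give 29–35% (outcome correlation 0.3–0.5, between-visit correlation 0.5–0.7). That is not the planned analysis: it drops the MANOVA, and the plan assigns the comparison of visits to maintenance.
- **Direction.** Hypothesis (i) is directional. Counting only false results in the programme's favour, at d = 0.33–0.5 and ρ = 0–0.5, gives about 8–12% with five null secondaries or 7–9% with four. The matching benchmark is then 2.5%, so the inflation remains.
- **Conjunction.** Read literally, hypothesis (i) requires all six effects, and that rule would inflate nothing. The plan does not state it.

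**Conclusion.** The plan leaves open which result decides hypothesis (i). That conclusion needs no simulation. MANOVA does not settle it, because an omnibus rejection can arise with no effect on depression, the only named primary.

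The size of the secondary-outcome problem is conditional. If MANOVA is followed by unadjusted 5% tests, the chance of at least one false secondary claim at a visit is about 4% when nothing works and roughly 9–22% when one outcome truly improves. The follow-up step, the effect (0.2–0.5 SD) and the correlations (0–0.7) are all assumed. The document sets no 5% target for the secondaries, so that comparison is with convention. The sample size of 340 is not in dispute here, though it was calculated for family functioning, a secondary outcome.

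This should be corrected before any analysis by arm. It affects what the trial can conclude, and the change is cheap.

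**What to change.** In Measures and Data Analyses:

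1. Replace the open wording on primary outcomes with: *The primary outcome is the PHQ-9.*
2. Name one deciding visit, one month or three months. Give it in months, because Study design numbers the assessments in two different ways.
3. State that hypothesis (i) is decided by the between-arm PHQ-9 comparison at that visit alone, at two-sided 5%, and not by the MANOVA omnibus test.
4. Keep hypothesis (ii) testable: test PHQ-9 between arms at the other visit at 5%, only if the first PHQ-9 test is significant.
5. Report the five secondaries as supportive, with estimates and 95% confidence intervals.
6. Optional, if confirmatory secondary claims are wanted: test the five with Holm's procedure at overall 5% after a significant PHQ-9 result. Steps 4 and 6 each spend 5%. For control across both, place the secondaries after the second PHQ-9 test, which costs further power.

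**Cost.** A few sentences and no new data. A secondary no longer supports hypothesis (i) by itself, and that includes family functioning, on which the 340 was sized. Under the option in step 6, power for a secondary with d = 0.33 falls from 80% to about 48–62%, or to 24–31% if the PHQ-9 effect is only 0.2. A sponsor unwilling to accept that can stop at step 5.

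### The plan lets an uncontrolled within-subject comparison count as a test of programme effect, with mislabelled time points and no rule on which test decides

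*Combined protocol and SAP*

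**What the plan says.** Under Study design: "The programme effects will be tested using both between-subject (comparison of the two arms) and within-subject" comparison. The parenthesis that follows describes the within-subject part as "comparison of measures at T1, T2, and T3". The same paragraph defines the schedule differently: "Assessments will be made before (T0), 1-month follow up (T1), and 3-month follow-up (T2"). There is therefore no T3, and T0 is not named in the within-subject comparison.

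Recruitment of participants makes eligible "parents with a score of Patient Health Questionnaire (PHQ-9) score of 2 or above". Measures states that "primary outcome variables include parental depression", and Table 1 gives the instrument for depression: "Measured by the Patient Health Questionnaire (PHQ-9, Kroenke et al., 2001), 9 items". Implementation and assessment adds: "After the first assessment (T0), caregivers who meet inclusion criteria will be randomized into Arm 1 or Arm 2". No separate screening visit is described.

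Data Analyses names one method, beginning "MANOVA will be used to evaluate the effects of the mindful", and applies it to Arm 1 relative to Arm 2 for primary and secondary outcomes. It adds a comparison of T1 with T2 for maintenance and mentions no control-arm contrast for it. No sentence ranks the between-subject test above the within-subject one.

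**The concern.** Parents selected because a score lies above a cut-off will, on average, score lower at the next measurement even if nothing is done. Distress linked to social unrest may also ease with time. Both processes act equally, in expectation, in two randomised arms, so they cancel in the comparison of Arm 1 with Arm 2. They do not cancel in a change from T0 within Arm 1, nor in a time effect pooled over both arms.

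The plan lists the within-subject comparison as a test of programme effect alongside the between-subject one and gives no rule for when they disagree. A fall within Arm 1 could then be reported as a programme effect when the arms do not differ. The wait-list control exists to close that route.

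**Working it through.** **1. The plan's own sample size, to fix the number analysed.** Inputs from Sample size estimation: effect size 0.33, two-sided 5%, power 80%, two independent groups, 15% drop-out. Equal allocation is assumed because the ratio is not stated.
- Per arm: 2 × (1.960 + 0.842)² / 0.33² = 144.2, rounded up to 145; total 290.
- With drop-out: 290 / 0.85 = 341.2, rounded up to 342. The t-test version gives 146 per arm and 292 / 0.85 = 343.5, rounded up to 344.
- The stated 340 reproduces within 3%. Completers: 340 × 0.85 = 289, or about 144 per arm.

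**2. Which contrasts are exposed.**

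| Contrast | Regression from T0 selection | Natural recovery |
|---|---|---|
| Arm 1 against Arm 2, or arm-by-time | cancels | cancels |
| T0 to T1 or T2 within Arm 1, or time pooled over arms | included | included |
| T1 to T2 within Arm 1 | absent | included |

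**3. Size of the regression, by formula (assumed inputs).** For a normal score with mean m, SD s and retest correlation r, selected above cut-off c, the expected fall is s(1 − r) φ(a)/[1 − Φ(a)], where a = (c − m)/s. Take c = 1.5 for a score of 2 or above.
- Example: m = 5, s = 4, r = 0.7. Then a = −0.875, φ(a) = 0.272, 1 − Φ(a) = 0.809 and the ratio is 0.336. The fall is 4 × 0.3 × 0.336 = 0.40 points.
- Over m = 3 to 7, s = 4, r = 0.6 to 0.85, the fall is 0.1 to 0.9 points (0.03 to 0.23 SD).

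**4. Size of the regression, by simulation (assumed inputs).** Correlated negative-binomial scores capped at 27; mean/SD of 4/4, 5/4.5 and 6/5; copula correlation 0.5 to 0.8; entry at 2 or above; 144 per arm; no treatment effect and no time trend.
- Mean fall 0.16 to 0.74 points (0.03 to 0.19 SD). The largest value comes from mean 4, SD 4, correlation 0.5; the smallest from mean 6, SD 5, correlation 0.8.
- Paired within-arm test from T0 significant at 5%: about 8% to 50% of trials.
- Between-arm test of change: near 5%.
- Adding an assumed 0.5-point natural recovery raises the within-arm rate to about 56-90%.

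**5. Sensitivity to the assumptions.** A different score model (mean 3 to 7, correlation about 0.4 to 0.9, 145 per arm) gives a fall of 0.2 to 1.4 points and within-arm rejection of 12% to 95%. The between-arm test rejects in 4% to 6% and a T1-to-T2 test in about 5% to 6%. The direction is stable; the size is not fixed by anything in the documents.

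**The case against.** The strongest reply is that the plan does not name T0 in the within-subject comparison. On its own definitions T1 and T2 both follow selection, so a literal T1-to-T2 test carries no regression from the entry screen and rejects at about 5% when there is no time trend. This stands for the literal reading. But T3 does not exist, the schedule has exactly three times, and a comparison made only after the programme could not show its effect. A shift of labels from T0, T1 and T2 is the likelier meaning. Even the literal test, within one arm, stays open to natural recovery.

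Second, hypothesis (i), the sample size and the MANOVA of Arm 1 relative to Arm 2 are all between arms. This also stands. A reader might infer that the plan will count spontaneous improvement as benefit, or that it gives the two tests equal weight. The documents support neither inference: no within-arm test from T0 is specified, and the tests are simply left unranked.

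Third, within-subject may only mean the time factor of a repeated-measures MANOVA, with the programme effect read from the arm-by-time term. That term would be protected, but the plan does not name it, and a time main effect pooled over arms would not be protected.

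Last, a cut-off of 2 is low, so the shift may be small. At the mild end of the assumed inputs it is (0.03 SD, about 8% false positives).

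**Conclusion.** The point holds as a conditional one. The plan admits a within-subject comparison as a test of programme effect, labels its time points wrongly and does not say which test decides. If that comparison includes T0, regression to the mean and natural recovery could be read as benefit on the primary outcome. Under assumed PHQ-9 inputs (mean 4-6, SD 4-5, correlation 0.5-0.8) the spurious fall is about 0.2-0.7 points, and a within-arm test in about 144 parents is significant in about 8-50% of trials. These figures show direction and plausible scale only.

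It also rests on T0 being both screen and baseline, which the text implies but does not say outright. The randomised comparison itself is sound on this point, and the sample size is unaffected. This is a cheap improvement to the plan, not a flaw in the trial's design.

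**What to change.** Three edits:
1. Correct the within-subject time labels to T0, T1 and T2.
2. State that programme effects, including maintenance at 3 months, are judged only on the between-arm difference at T1 and T2 adjusted for T0, or equivalently on the arm-by-time term. For T2 this assumes that the wait-list arm has not yet had the programme, which the documents do not state; the plan should say whether that is so.
3. Report within-arm changes, including T1 to T2, descriptively as a mean with 95% CI and no efficacy claim.

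The cost is a few sentences. No extra data or participants are needed. The only loss is that within-arm p-values can no longer support an efficacy claim.

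### The stated 80% power is for a two-group test of one outcome and is not shown to apply to the MANOVA, the only between-arm analysis the plan names

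*Combined protocol and SAP*

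**What the plan says.** The sample size paragraph under Study design states: "An estimated 340 parents will be recruited and randomised into an intervention group and a waitlist control group". The basis is an "expected effect size of .33 for family functioning in the PI's pilot study", a drop-out rate of 15%, and "a two-tailed α error of 5%, 80% power, and a test of two independent groups". This describes one comparison of two arms on one outcome.

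The Measures section says that "primary outcome variables include parental depression". It lists five secondary outcomes: anxiety, post-traumatic stress, family functioning, family conflict and interpersonal mindfulness. That makes six outcomes in all.

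Data Analyses then states that "MANOVA will be used to evaluate the effects of the mindful" parenting arm relative to the waitlist arm, and for "the analyses of the primary and secondary outcome measures". It adds a comparison of T1 with T2 to assess maintenance. It names no other between-arm test. It does not say whether the six outcomes enter one joint test, how the visits enter, or which tests follow the MANOVA. No correlations between outcomes are given, and no effect sizes for the other five.

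**The concern.** The sizing and the analysis describe different statistics. A two-group test of one outcome has one numerator degree of freedom, and its power depends on one effect size. A joint MANOVA of six outcomes has six numerator degrees of freedom. Its power depends on the whole set of effects and on how the outcomes correlate, and the sizing uses neither.

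Two things are at stake. First, a reader of a null MANOVA would interpret it at 80% power, although nothing in the documents shows that the test has that power. Second, an omnibus test answers a different question: it can be significant because of any combination of the six outcomes, so a positive result would not show that depression improved.

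This is separate from the question of which outcome was sized. It would remain if .33 were an effect on the PHQ-9.

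**Working it through.** **Inputs from the documents.** 340 randomised; effect .33; drop-out 15%; two-tailed 5%; 80% power; six outcomes.

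**Assumptions.** .33 is a standardised mean difference (the metric is not named). Allocation is 1:1 (no ratio is given). The effects on the other outcomes and a common correlation ρ are assumed, because the documents give none.

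**Step 1: reproduce the printed figure.**
- Normal approximation: n per arm = 2(1.96 + 0.8416)²/0.33² = 144.1, so 145 per arm and 290 in total. 290/0.85 = 341.2, so 342 randomised.
- t-test: 145.1, so 146 per arm and 292 in total. 292/0.85 = 343.5, so 344 randomised.
- In reverse: 340 × 0.85 = 289 analysed, or 144.5 per arm. Power is 79.8% (t) or 80.1% (normal).

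The printed 340 is therefore consistent with a single-outcome, two-group test.

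**Step 2: power of a two-group MANOVA on the same 289.** This is Hotelling's T². Its power comes from a noncentral F with p and N − p − 1 degrees of freedom and noncentrality λ = (n₁n₂/N)·D², where D² = δ′R⁻¹δ. Here δ holds the standardised effects and R the correlations. With N = 289, n₁n₂/N = 144.5²/289 = 72.25. For p = 6 the degrees of freedom are 6 and 282. Power of 80% needs D² of about 0.193.

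*Least favourable case with .33 on one outcome.* With one effect fixed at .33, D² is smallest when each other outcome shifts by exactly ρ × .33. Then D² = 0.33² = 0.1089 whatever ρ is, λ = 72.25 × 0.1089 = 7.87, and power is 51%. At ρ = 0 this means no shift in the other five. For 80% power this case needs about 508 analysed, and 508/0.85 gives about 598 randomised.

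*Other patterns.* With .33 on all six, D² = 6 × 0.1089/(1 + 5ρ). With .33 on one and zero on five, D² = 0.1089 × (1 + 4ρ)/[(1 − ρ)(1 + 5ρ)].

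| Pattern of effects | ρ = 0 | 0.3 | 0.5 | 0.7 |
|---|---|---|---|---|
| .33 on one, ρ × .33 on five | 51% | 51% | 51% | 51% |
| .33 on one, zero on five | 51% | 63% | 79% | 96% |
| .33 on one, .20 on five | 96% | 63% | 53% | 53% |
| .33 on all six | >99% | 92% | 79% | 66% |

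The last row stays at or above 80% up to ρ of about 0.48, since (6 × 0.1089/0.1928 − 1)/5 = 0.478.

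**Step 3: another reading of MANOVA.** Suppose it is run for each outcome separately, with T1 and T2 as the two responses and .33 at both visits. Then D² = 2 × 0.1089/(1 + ρ), where ρ is now the correlation between visits. Power is 88%, 83% and 78% at ρ = 0.3, 0.5 and 0.7.

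**The case against.** A reader might infer that the trial lacks its stated power for the analysis it will run. The documents do not support that. Hypothesis (i) expects benefit on all six outcomes. If each shifts by .33 and the correlations are modest, a joint MANOVA has more than 80% power. The 51% figure is a mathematical floor given .33 on one outcome, not a forecast. It also should not be described as the power whenever one outcome carries the effect: if the other five do not move at all, 51% holds only at zero correlation, and power rises to 96% at a correlation of 0.7.

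The wording of Data Analyses is also open. It never says that one omnibus test of six outcomes decides the trial, and the per-outcome reading in Step 3 shows little or no shortfall. Sizing on a simple two-group test while planning a multivariate analysis is a common simplification.

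All of this stands against a claim of a proven shortfall. It does not remove the mismatch. Hypothesis (i) predicts direction and not equal size: with .33 on one outcome and .20 on the other five, power is 63% at a correlation of 0.3 and 53% at 0.5. The per-outcome MANOVA is not the test that was sized either. On any reading, the plan does not say which test its 80% describes.

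**Conclusion.** The concern holds as a gap in specification, not as an arithmetic error. The 340 is correctly derived for a two-tailed 5% test of one outcome at .33 with 289 analysed. The plan does not show that the 80% carries over to the MANOVA.

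If all six outcomes enter one MANOVA, power is undetermined from the documents, and both shortfall and surplus are possible within the range shown in the table. These figures rest on a standardised effect of .33, equal arms, 289 independent observations, and assumed effect patterns with a common correlation.

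The second part does not depend on those assumptions: a significant joint test of six outcomes would not establish an effect on depression.

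**What to change.** Make a two-sided 5% comparison of Arm 1 and Arm 2 on the one primary outcome the deciding test, and keep MANOVA as a supportive analysis. In the sample size paragraph, state that 80% power applies to that single-outcome test with 289 analysed, on the condition that .33 holds for that outcome. The condition is needed because .33 is given for family functioning and no effect size is given for depression.

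If MANOVA stays the deciding test, say which outcomes and visits enter it. Replace the 80% with its power at 289 over a stated range of effect patterns and correlations, and label 51% as the least favourable case with .33 on one outcome when six outcomes enter jointly.

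The cost is protocol wording and, if MANOVA is kept as decisive, one recalculation. Neither option by itself calls for more participants or data. The downside is that MANOVA loses its deciding role, or the stated power becomes a range that may fall below 80%.
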